Specific Aim 1: To compare abstinence rates among AA non-daily smokers receiving either smoking cessation counseling (C) or smoking cessation counseling in combination with NRT (C+NRT). Hypothesis: Participants randomized to C+NRT will have significantly higher biochemically verified smoking abstinence than participants randomized to C at 12 weeks end of treatment (primary outcome) and at 26 week follow-up. Analytic strategy: The chi-square test will be used to compare the verified abstinence rates at Week 12 (primary cessation endpoint) and Week 26 (secondary cessation endpoint) between C and C+NRT. For our primary comparison, those lost to follow-up will be considered as smokers. Assuming the expected treatment effect, we will descriptively examine the cessation rate within the C+NRT group by choice of NRT. A statistical comparison will not be conducted as we do not know a priori who will choose what and the choice will not be random. We also will look at completers only and will utilize multiple imputation techniques to ensure valid comparisons between the two groups if the loss to follow-up is not random. Secondly, we will utilize Generalize Estimating Equation methodology to longitudinally compare verified abstinence. We will then examine the effects

of the covariates and patient and provider outcomes listed in the measurement table above on this endpoint by utilizing best subsets selection techniques. Our goal is to identify a final model utilizing the smallest subset of covariates that describes cessation over the length of the study. Given the sample size and expected cessation rate, we anticipate a model that contains at most six covariates. We expect no difference in the distribution of demographic and smoking history covariates between groups and we will not statistically compare those as per CONSORT recommendations for randomized clinical trials. Within the NRT treatment group, we will examine the effect of NRT adherence over the first 12 weeks on verified cessation using logistic regression.

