
These doses represent a starting point. To enhance the ability of our findings to be translated into practice, counselors will educate participants about the relationship between cpd and NRT dosing and empower them to tailor use to be consistent with their smoking patterns, intensity of withdrawal and craving, and level of side effects. Participants will be taught that, if the NRT dose is adequate, they may still have urges during the day, but most of the time they will not feel strong physical cravings or discomfort. They will also be educated about side effects that may indicate a nicotine overdose (nausea, vomiting, cramps, dizziness) and the need for a dose reduction (i.e., fewer pieces of gum/lozenge per day, reduction from 24 to 16 or 12 hours per day that the patch is worn), as well as symptoms of withdrawal (e.g., irritability, restlessness, anxiety) and strong physical craving that may indicate the need for a dose increase (i.e., more pieces of gum/lozenge per day, increase to longer wear or a higher dose patch). Counselors will probe for smoking level, use of NRT (days used, amount used per day), side effects, symptoms of withdrawal and craving, and general experiences with the

medication during the week 1, 4, 6, 8, and 10 sessions and will provide guidance, as necessary, to ensure that the medication is working optimally for each participant. The PI and study physician will provide oversight on questions and issues that arise related to side effects, dose reductions and/or increases.

Overview of Major Study Events

		Enroll./ Baseline					EOT	Final Follow- Up
		Wk 0*	Wk 1	Wk 4	Wk 8	Wk 10	Wk 12*	Wk 26*
Screening/ Assessments	X	X		X	X		X	X
Intervention								
Counseling		X	X	X	X	X		
Medication Dispensing (C+NRT only)		X (3 to 9- day trial period)	X	X	X		X	

*in person; all other visits are by telephone; EOT=end of treatment

Procedures and Methods

An overview of major study events is provided in the adjoining table.

Initial Screening.

The initial screen will review inclusion/exclusion criteria. Those eligible will be scheduled to complete final eligibility screening within 14 days. All ineligible smokers will be referred to local resources.

Final Screening and Enrollment (Wk 0). Final eligibility screening will be conducted in person and will consist of a pregnancy test on women of childbearing age and obtaining informed consent.

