Smoking abstinence at Wk 12 (primary cessation outcome) and Wk 26 (secondary cessation outcome). Biochemically confirmed at Wk 12 using urine anabasine and anatabine, with the recommended cut-off of 2 ng/ml to differentiate smokers from non-smokers. ⁵⁰ These tobacco alkaloids are considered the gold standard for confirming abstinence when cotinine measurements are not valid – i.e., detectable levels of cotinine could reflect NRT use or smoking. ⁵⁰ Biochemically confirmed at Wk 26 using urinary cotinine, the proximate metabolite of nicotine, with the recommended cut-off of 50 ng/ml used to differentiate smokers from non-smokers. ⁵¹ Time Points: Wk 12, 26
Secondary Patient- and Provider-Derived Outcomes (Aim 2)
Nicotine intake (total nicotine equivalents/creatinine). Assessed by urine; quantified by examining the sum of four of the major nicotine metabolites (cotinine + cotinine-glucuronide + trans-3'-hydroxycotinine + 3HC-glucuronide) to creatinine ratio using procedures described by [name] (consultant). ⁵¹ Total nicotine equivalents/creatinine represents the current gold standard for estimating nicotine intake/exposure from tobacco. ⁵⁷ To ensure that nicotine metabolites detected at Wk 12 are a result of tobacco exposure and not NRT use, we will schedule the urine collection for 7 days after the last dose of NRT. This 7-day time frame is more than adequate given the 15-20 hour (3-4 day) elimination half-life of cotinine and accounts for the substantial individual variability in the rate of elimination of nicotine. ⁵⁸ Time Points: Wks 0,12,26
Carcinogen exposure [NNAL, PAH]. Assessed by urine; quantified by examining NNAL (4-(methylnitrosamino)-1-(3)pyridyl-1-butanol) and polycyclic aromatic hydrocarbons (PAH) and specifically, 1-hydroxypyrene (1-HOP), using procedures described by [name] (consultant). ⁴⁰ While there are >70 established carcinogens in tobacco, NNAL and PAH are widely considered to be among the most important causative agents in the development of lung and esophageal cancer ^{38,39,59} and reflect the current gold standard for estimating carcinogen exposure from tobacco products. Time Points: Wks 0,12,26
Days Abstinent. Cumulative number of days abstinent Time Points: Wks 1,4,8,10,12
NRT adherence. 3-day recall of NRT use (C+NRT only) -- i.e., pieces of gum, lozenge, or number of patches used in the last 3 Time Points: Wks 4,8,12

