Confidentiality will be maintained by assigning each participant a study identification number and numerically coding all data. The association of the ID-code and the participant's name will be kept by [name] in a locked file cabinet. The screening questionnaire and all survey data will be directly entered into RedCap or CRIS and accessible only by study staff. Any paper copies of records will be kept in a locked filing cabinet in offices that are kept locked when unoccupied. Only summaries of group data will be reported in any publications or presentations, with no identification of individuals. Because identifiable information will be collected, participant privacy will be maintained throughout the duration of the study by adhering to the regulations set forth by the HIPAA Privacy Rule. More specifically, identifiable information will not be released without written authorization of the participant.

Mobile devices will not be used for data collection or storage. Identifiable data will not be sent outside of KUMC.

B. Sample / Specimen Collection

No more than 30 ml of urine will be collected at Weeks 0, 12, and 26. Urine will be de-identified, labeled with a study identification number, and stored at the Bioanalytical Laboratory at the Fairway Clinical Research Center under the direction of [name]. Samples will be accessible only to members the study team. Results from biomarker analyses will be de-identified and shared only with members of the research team. Any resulting publications will present the data in aggregate; individual participants will not be identified. Samples will be disposed of one month after the final report is sent out to the Principal Investigator, unless participants agree to have their urine stored for future testing. For participants who agree to future testing, samples of their urine will be stored indefinitely.

C. Tissue Banking Considerations

For participants who agree to future testing, samples of their urine will be stored indefinitely. New markers of nicotine and carcinogen exposure are being discovered and the stored urine samples would be used for analysis of these new markers. All samples stored for future biomarker analyses will be de-identified and accessible only to members of the study team. Results from these analyses will be de-identified and shared only with members of the research team. Any resulting publications will present the data in aggregate; individual participants will not be identified.

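### A 3-day NRT recall taken at the Wk 12 urine visit would fall inside the planned 7-day NRT-free interval, leaving two informative adherence time points instead of three

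*Combined protocol and SAP*

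**What the plan says.** Section II.B of the combined protocol and SAP lists NRT adherence as a secondary outcome. The Measure and Assessment Time Points table (II.E) measures it by "3-day recall of NRT use (C+NRT only) -- i.e., pieces of gum, lozenge, or number of patches used in the last 3" days, at Wks 4, 8 and 12. No scoring rule is given: there are no weights for the three points, no denominator, and no instruction on NRT-free days.

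The Nicotine intake row of the same table fixes the timing of the Wk 12 sample: "we will schedule the urine collection for 7 days after the last dose of NRT". Its stated purpose is: "To ensure that nicotine metabolites detected at Wk 12 are a result of tobacco exposure and not NRT use". Section IV.B adds: "No more than 30 ml of urine will be collected at Weeks 0, 12, and 26". The Overview of Major Study Events shows one Wk 12 contact, held in person, labelled end of treatment and marked for assessments.

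The adherence measure is then used in II.C, Specific Aim 1, within the NRT arm: "we will examine the effect of NRT adherence over the first 12 weeks on verified cessation using logistic regression".

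A second, informal source of data on NRT use appears under NRT dosing (II.E): "Counselors will probe for smoking level, use of NRT (days used, amount used per day), side effects". The sessions named there include Wk 10 but not Wk 12, and these probes are not called the adherence measure.

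The documents do not agree on when NRT ends. A 12-week supply is chosen after a 3 to 9-day trial. The events table, as extracted, marks dispensing at Wk 12. The counseling table mentions ending medication in connection with Wk 10. The abstinence row uses anabasine and anatabine at Wk 12 because cotinine could come from NRT.

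**The concern.** A 3-day look-back fits wholly inside a 7-day NRT-free interval. If the adherence question is asked at the visit where that urine is collected, a participant who has done everything asked reports no NRT use. Nothing in the plan ties the Wk 12 question to the last days on treatment, and nothing removes the NRT-free days from the score.

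What is at stake is one of three time points of a named secondary outcome, and the predictor in the Aim 1 adherence regression. That regression claims to cover the first 12 weeks, yet its formal data would stop at Wk 8. If some participants have stopped NRT by Wk 12 and others have not, the Wk 12 item would record who had stopped rather than who had been adherent.

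**Working it through.** **1. The plan's own figures.** The plan computes nothing for adherence. Its only design calculation is the power of the chi-square test with 128 and 256 participants (II.C). With pooled variance, power = Φ[(d − 1.96·SE0)/SE1]. For 10% vs 25%:
- d = 0.15 and the pooled rate is (12.8 + 64)/384 = 0.20.
- SE0 = √(0.20 × 0.80 × (1/128 + 1/256)) = 0.0433.
- SE1 = √(0.09/128 + 0.1875/256) = 0.0379.
- Power = 95.7%.

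The same formula gives 87.6% for 22.5% and 71.7% for 20%. The stated 95%, 87% and 71% are reproduced. None of them depends on adherence.

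**2. Day count.** Take Wk 12 as day 84 and let the recall cover the 3 days before the visit. Last dose = urine day − 7.

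| Reading | Last NRT dose | Urine | Recall covers | NRT days recalled |
|---|---|---|---|---|
| Shared visit on day 84, interval observed | 84 − 7 = 77 | 84 | 81–83 | 0 of 3 |
| 84-day supply after 3-day trial, whole visit moves | 3 + 84 = 87 | 94 (Wk 13.4) | 91–93 | 0 of 3 |
| 84-day supply after 9-day trial, whole visit moves | 9 + 84 = 93 | 100 (Wk 14.3) | 97–99 | 0 of 3 |
| Same supply, only the urine moves | 87–93 | 94–100 | 81–83 | 3 of 3 |
| Shared visit on day 84, NRT still in use | after day 83 | 84 | 81–83 | 3 of 3, but the urine rule is not met |

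The recall is zero whenever it shares the urine visit and the interval is observed. It is informative only if recall and urine fall on different dates, or if the interval is not kept.

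**3. Coverage.** Planned: 3 points × 3 days = 9 of 84 days. With an uninformative Wk 12: 2 × 3 = 6 of 84 days, none after Wk 8.

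**4. Illustrative score.** This assumes equal weights and a constant six pieces/day, the starting amount for gum or lozenge. Perfect use is 6 × 3 = 18 pieces per window.
- With the interval: (18 + 18 + 0)/9 = 4.0 pieces/day, and 4.0/6 = 67%.
- Without it: (18 + 18 + 18)/9 = 6.0 pieces/day, or 100%.

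**5. Effect on rankings.** Let a4 and a8 be the fractions of the daily amount used at Wks 4 and 8.
- If everyone stops on schedule, score = (a4 + a8 + 0)/3 = ⅔ × (a4 + a8)/2. This is a constant rescaling of the two-point mean. Order is unchanged. The logistic coefficient per unit is 1.5 times larger, with the same fit and p-value as a regression on the Wk 4 and Wk 8 mean.
- If stopping is mixed, a constant user at fraction u scores ⅔u after stopping and u while continuing. Under the step 4 assumptions, someone using 70% throughout and still using at Wk 12 scores 70%, above the 67% of a perfect user who stopped.

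**The case against.** The strongest reply is that the zero is conditional. The plan schedules the urine, not the adherence interview, 7 days after the last dose, and no sentence puts both on the same day. This stands as a condition. The single in-person Wk 12 visit makes a shared date the natural reading, and no split is planned, but the zero should not be stated as unconditional.

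A reader might infer that anyone using NRT at Wk 12 is breaking the schedule. The documents do not support that. A 12-week supply begun after the trial period, dispensing marked at Wk 12 and the choice of tobacco alkaloids for verification all allow for use at that time. Continued use does not rescue the plan, though: the recall then works, but the interval protecting the Wk 12 nicotine-intake measure fails.

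A reader might also infer that the score puts participants in the wrong order as a matter of course. It does so only with a mix of stoppers and non-stoppers, and the documents give no proportion. Nor is the gap between 67% and 100% a predicted bias: the plan defines no score, and participants may tailor their dose.

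Two further limits stand. The Wk 10 counselor probe means NRT use after Wk 8 is not wholly unobserved, although no formal measure exists there. The Aim 2 summary is the percentage in each product group who used their chosen product during treatment. Anyone reporting use at Wk 4 or 8 could already count, so a Wk 12 zero need not alter it.

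**Conclusion.** The point holds in conditional form. If recall and urine share the Wk 12 visit and the 7-day interval is observed, the Wk 12 adherence value is zero for every participant who follows the schedule. Formal coverage then falls from 9 recalled days to 6, and ends at Wk 8.

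The consequence depends on behavior at Wk 12. With uniform stopping, absolute adherence is understated and the ranking is intact. With mixed stopping, continuing users score above equally adherent stoppers, and the Aim 1 adherence regression can be biased. The direction is not established. The counseling section has counselors encourage those who have not quit to keep using NRT, so a link between high Wk 12 scores and not quitting is plausible, but the documents do not show it.

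The damage is confined to a secondary outcome and a non-randomized, within-arm regression. The primary comparison and its power do not change. The correction is still worth making, because following both rows of the table as written makes one of three measurements uninformative and the remedy is cheap.

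**What to change.** - Word the Wk 12 item to ask about the 3 days before the last NRT dose, and record the date of that dose. Alternatively, take the third 3-day recall at the existing Wk 10 call instead of at Wk 12.
- State that planned NRT-free days do not count in the adherence score or in the Aim 1 adherence regression, and write down how the three points are combined.
- Reconcile the statements on when NRT ends: the 12-week supply after a 3 to 9-day trial, the dispensing mark at Wk 12, the counseling-table reference to Wk 10, and urine 7 days after the last dose. Say whether recall and urine are taken on the same date. Which timing is right is for the investigators to settle.

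Cost: no extra visit. The Wk 12 option needs a reworded item and one date field, and the recall reaches back about 10 days (a 7-day interval plus 3 days). The Wk 10 option adds one item to a call that already records days abstinent and probes NRT use, although the events table marks no assessment there.

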Specific Aim 2: To compare patient- and provider-desired outcomes -- e.g., nicotine intake, carcinogen exposure, number of days abstinent, and side effects – among AA non-daily smokers receiving C versus C+NRT and, within the C+NRT group, examine the choice of NRT and use during the treatment period. Hypothesis: Participants randomized to C+NRT will demonstrate significantly greater reductions in nicotine intake and carcinogen exposure and significantly more days abstinent, while experiencing no differences in side effects as participants randomized to C. Analytic strategy: We will utilize linear mixed models to longitudinally (week 12 and 26) compare nicotine and carcinogen exposure between the two groups, then subsequently examine the effects of the covariates listed in the measurement table above using a best subsets selection method for both nicotine and carcinogen exposure independently. A generalized linear mixed model approach will be used to model days abstinent, controlling for number of days in study, to assess the effect of treatment on this endpoint and best subsets selection will be used to examine the effects of covariates on this endpoint. For each of these models, based upon the sample size, we anticipate that ten to twelve covariates could be included in a final model. We will compare the prevalence of any side effect as well as each specific side effect, from baseline to week 12, between the two groups using the chi-square test. If there is a global difference we will examine, within the NRT group, if type of NRT impacts the side effect profile. Within the NRT group we will descriptively summarize the number and percent of subjects who choose each type of NRT. Subsequently we will describe and descriptively compare the percent of subjects within each of these subgroups who use the NRT of choice during the treatment period (i.e., percent of patients within the patch, gum, and lozenge groups who used the medication).

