NRT (C+NRT). Participants randomized to C+NRT will be given their choice of nicotine gum, patch, or lozenge to try for 3 days each. After the 3 to 9-day trial period, they will select and receive a 12 week supply of the medication of their choice. Similar NRT choice trials have been used successfully by others.⁵² This patient-centered approach was informed by our Patient Advisory Panel, who preferred these medications because of cost and over the counter availability, and our Stakeholder Advisory Panel, who felt that this patient-centered approach emulated clinical practice and would broaden the implications of our study for informing evidence-based guidelines for treating tobacco dependence in AA non-daily smokers. Nicotine gum, patch, and lozenge are all highly effective first-line medications approved for the treatment of tobacco dependence that have been shown to double the rate of quitting compared to placebo.^{11,28} NRT dosing. One of the clinical implications of this study is to inform the development of NRT dosing guidelines for non-daily smokers. We will work hand-in-hand with our providers and quitline experts to ensure that the counseling and NRT dosing protocols can be easily implemented with non-daily smokers in clinical practice and through the national quitline, Alere. We draw on our decades of experience treating AA smokers, the well-established literature on nicotine metabolism among AA smokers, and expert consensus to derive NRT dosing guidelines. Urine cotinine levels from AA daily smokers are consistent with taking in the equivalent of 8-10 mg of nicotine per day.⁴⁰ Urinary cotinine data from our NDS pilot study indicate that AA non-daily smokers have an average daily intake of cotinine that is 61% that of daily smokers or equivalent to 5.5 mg of nicotine per day.³⁵ The goal of treatment with NRT is to replace most or all of the nicotine that would have been obtained from tobacco with nicotine from the replacement product. However, not all nicotine from NRT is absorbed into the system. For a 7 mg patch, approximately 5 mg of nicotine is absorbed.⁵³ Likewise, for each 2 mg gum or lozenge, only 1 mg of nicotine is absorbed.⁵⁴ Following from the absorption rates of these products and our preliminary data indicating that AA non-daily smokers are in need of at least 5.5 mg of replacement nicotine per day, participants choosing the patch will be started on one 7 mg patch/day and those choosing gum/lozenge will be started on six 2 mg pieces/day.

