Counseling Visits (Wks 0,1,4,8,10). Counseling sessions will be completed by phone at Wks 1,4, 8,10, and in person at Wk 0. The number of sessions is consistent with our previous studies where we have achieved visit completion rates of around 80%.^{45,55,56}

NRT Dispensing (Wks 0-1). Participants randomized to C+NRT will be given a trial supply of nicotine gum, patch, and lozenge and be instructed to try each for 3-days. After the 3 to 9-day trial period, they will select and be mailed a 4 week supply of the medication of their choice. They will receive refills of their selected medication at the Weeks 4 and 8 study visits.

Biological Sample Collection (Wk 0,12,26). Urine will be collected three times throughout the study for biochemical verification of cessation at Wk 12 and Wk 26, nicotine intake at Wks 0, 12, 26, and carcinogen exposure at Wks 0, 12, and 26. Additional details regarding each assay are provided in the Measures and Assessment Time Points table.

Retention. We have developed a system of reminders and compensation that have resulted in impressive retention rates in our previous clinical trials. Reminders. One week prior to each scheduled visit a reminder postcard noting the scheduled appointment date and time will be mailed to participants. In addition, participants will be called up to 6 times to remind them of their upcoming visit. A detailed tracking database, with an automated reminder system, will notify counselors of when to send postcards and complete reminder phone calls. Compensation. Participants will be given a \$40 electronically loaded gift card at Wks 0, 12 and a \$20 electronically loaded gift card at Wks 1, 4, 8, 10, 26 in appreciation for their time and participation.

Measures

Our selection of measures (see table) and the measurement time points have been driven by our patient and stakeholder advisory panels.

Measure and Assessment Time Points

Primary Scientific Outcome (Aim 1)

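### The only listed measure of NRT use, a 3-day recall at Wks 4, 8 and 12, cannot separate people who stopped their chosen product early from people who never started it

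*Combined protocol and SAP*

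**What the plan says.** All references are to the combined protocol and SAP.

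- **Measure.** The NRT adherence row of the Measure and Assessment Time Points table (section II.E) specifies a 3-day recall in the C+NRT arm: "pieces of gum, lozenge, or number of patches used in the last 3 Time Points: Wks 4,8,12". No other measure of NRT use is listed.
- **Aim 1 use.** In section II.C, within the NRT arm, "we will examine the effect of NRT adherence over the first 12 weeks on verified cessation using logistic regression".
- **Aim 2 use.** Section II.C also describes, over the treatment period, the "percent of patients within the patch, gum, and lozenge groups who used the medication".
- **Counselor questions.** The dosing text in II.E says: "Counselors will probe for smoking level, use of NRT (days used, amount used per day), side effects", at sessions in weeks 1, 4, 6, 8 and 10. The measures table does not list the answers, and no analysis names them.
- **Supply.** Participants try the products first. "After the 3 to 9-day trial period, they will select and be mailed a 4 week supply of the medication of their choice", with refills at Weeks 4 and 8. The intervention text gives the total: "they will select and receive a 12 week supply of the medication of their choice".
- **Washout.** The nicotine-intake row places the Wk 12 urine collection seven days after NRT has ended.

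The plan defines neither an adherence score nor who counts as having used the medication.

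**The concern.** Both analyses ask about the whole treatment course, but the measure sees three short windows, the first near the end of week 4. Early use followed by stopping leaves no trace in it. Use would be understated, and early stoppers would be pooled with people who never opened the chosen product.

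This matters for interpretation. If C+NRT shows little benefit, the reader needs to know whether the product was never taken up, was taken up and dropped, or was used and did not help. The listed recall cannot distinguish the first two. NRT adherence is also a named secondary outcome in II.B, and informing NRT dosing for non-daily smokers is a stated purpose in II.E. Early use that is not recorded cannot be reconstructed after data collection.

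**Working it through.** The plan states no coverage figure for NRT use, so there is none to reproduce. Its power figures do not enter this point.

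**Inputs**
- Recall length of 3 days, at Wks 4, 8 and 12 (measures table).
- Treatment length of 12 weeks = 84 days (NRT paragraph, II.E).
- Trial period of 3 to 9 days before product choice (NRT Dispensing, II.E).
- Urine seven days after the last NRT dose (nicotine-intake row).
- Week w is taken as day 7w from Wk 0.

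**Coverage**
- 3 recalls × 3 days = 9 days; 9/84 = 10.7%.
- If the Wk 12 recall is taken at the post-washout visit, its three days contain no NRT by design. That leaves 2 × 3 = 6 days; 6/84 = 7.1%. So 9 is a maximum.

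**First sampled day**
- Wk 4 is day 28, so the first window is days 26-28 (25-27 if the visit day is excluded).
- Days 1-25 are never sampled: 25/84 = 29.8%.

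**The same gap on the chosen product's clock**
- Choice after 9 days of trial: 25 − 9 = 16 unsampled days.
- Choice after 3 days of trial: 25 − 3 = 22 unsampled days.
- Mailing time would shorten these somewhat.

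**Illustration of who is missed**

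The documents give no stopping-time data. Assume permanent stopping with exponential times from product choice and median m days. The share stopped before the first window is 1 − 2^(−d/m), where d is the number of unsampled days.

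| Median use | d = 16 | d = 22 |
|---|---|---|
| 12 weeks (84 d) | 1 − 2^(−16/84) = 12.4% | 1 − 2^(−22/84) = 16.6% |
| 6 weeks (42 d) | 1 − 2^(−16/42) = 23.2% | 1 − 2^(−22/42) = 30.4% |
| 4 weeks (28 d) | 1 − 2^(−16/28) = 32.7% | 1 − 2^(−22/28) = 42.0% |

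**Would more 3-day windows be enough?** The same recall at Wks 1, 4, 8, 10 and 12 covers 5 × 3 = 15 of 84 days (17.9%), starting at days 5-7. A count of days used since the last contact would in principle cover the whole period.

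**The case against.** Several objections have force.

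- **No scoring rule.** A reader might infer that the plan classes early stoppers as non-users. The documents do not say so, because no score or user definition is written. What follows from the text is narrower: such a person has zero use on every listed recall.
- **The clock.** Counting 25 unsampled days from Wk 0 would give 19%, 34% and 46% for the three medians. For the chosen product that is too high, because it mixes trial days with days on the selected product. The 16-to-22-day range is the right one here.
- **Assumed stopping.** The percentages depend on an assumed distribution and on permanent stopping. Counselors encourage people who are still smoking to continue NRT, and refills come at Weeks 4 and 8. Someone who restarts could appear in a later window.
- **Never tried.** A reader might infer that a product with early drop-off would look untried. It would not: participants are told to try each product before choosing, and the choice itself is a listed variable.
- **Short recall has merits.** Low coverage is not bias in itself. Three windows can describe use around Wks 4, 8 and 12, and a 3-day recall is more exact for amount. The panels drove the time points, and limiting the number of items is a stated aim.
- **Limited reach.** The affected analyses are one within-arm regression and one descriptive summary.

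These points narrow the claim but do not remove it. The two analyses are worded for the whole course, and the listed measure has no view of the first weeks on the chosen product. The burden argument is weak, because the counselor question is already asked and cumulative days abstinent is already collected at Wks 1, 4, 8, 10 and 12.

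**Conclusion.** The concern holds in a limited form. Adherence across the 12 weeks, and the percent who used their chosen product at any time in treatment, cannot be recovered from the listed measure. Anyone who stopped for good before about day 26 is indistinguishable from someone who never started. This would change only if the counselors' answers were recorded and used, which the plan does not say.

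The coverage counts follow from the documents, taking weeks as nominal days from Wk 0. The drop from 9 to 6 sampled days depends on the Wk 12 recall being taken at the post-washout visit. The 12-17%, 23-30% and 33-42% figures show how the loss scales under assumed stopping; they do not estimate what will happen in this trial.

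A reader might take this as a threat to the main result. It is not: the primary intent-to-treat comparison and its power do not use NRT-use data. This is an inexpensive improvement to secondary analyses, and it has to be made before the data are collected.

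**What to change.** 1. **Record the existing probe.** Make the counselors' questions a study measure at Wks 1, 4, 8 and 10, and ask the same at Wk 12: days NRT was used since the last contact, and usual amount per day. Update the measures and events tables to match.
2. **Separate trial use from chosen-product use.** The Wk 1 contact may fall inside the trial period, so record the date of product choice and keep the two kinds of use apart.
3. **Write the definitions.** Adherence: the share of days with use from product choice to the planned end of NRT, excluding the pre-urine washout. Used the medication: any reported use of the chosen product since selection.
4. **Keep the 3-day recall** as a check on amount. Have the Wk 12 recall refer to the last three days before the washout.
5. **Reconcile the schedule.** The dosing text names a week 6 session, whereas the counseling schedule has Wks 0, 1, 4, 8 and 10. The changes above do not rely on week 6.

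The cost is one extra data field per contact and a few lines of analysis-plan text, with no new contact. The downside is that recall over one to four weeks is less exact for amount, which is why the 3-day recall stays.
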